August 16, 2022

Do Generic Volar Locking Plates Provide Similar Outcomes at a Reduced Cost?

Study Protocol and Statistical Analysis Plan

Study Narrative

1. Summary

Distal radius fractures are a common injury in the community. When treated with open reduction internal fixation (ORIF), the volar locking plate (VLP) is the most frequent implant used. Current literature has shown most orthopaedic surgeons are unfamiliar with construct costs. Many surgeons use implants the hospital provides and have no preference for one implant company's plate over another. Previous studies have demonstrated increased implant costs do not increase patient reported outcomes (PROs) in other injury patterns. Generic implants can potentially reduce total procedural costs and not negatively impact patient outcomes. With an increasing emphasis being placed on providing high-value care to patients, and rising healthcare costs, there is a need to pursue more economical means of treating distal radius fractures. Additionally, with the increasing volume of distal radius fractures with a growing elderly population, it is important to consider adoption of an already partially implemented process. Some surgeons today in our health system use the generic VLP, with little apparent differences in reoperation rates and complications. Validation of its safety and efficacy on a larger scale could support its adoption as a universal stand of practice, thus reducing cost to the patient and hospital.

2. Study aims:

- a. Primary:
 - i. To determine if there is any difference in 90-day reoperation rate between patients treated with a generic or conventional volar locking plate.
 - ii. To determine if there is any difference in 90-day readmission rate between patients treated with a generic or conventional volar locking plate.
 - iii. To determine if there is any difference in 90-day mortality rate between patients treated with a generic or conventional volar locking plate.

- b. Secondary:
 - i. To determine if generic implants have a lower cost than conventional implants.
 - ii. To determine any differences in estimated blood loss by implant type (generic vs. conventional).
 - iii. To determine tourniquet time by implant type (generic vs. conventional).

3. Background, Rationale, Significance

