- a. Healthcare costs continue to rise in the United States, while Medicare reimbursement rates are declining (Haglin JOT 2021). With that, orthopaedic surgery is becoming a common target of cost containment strategies as musculoskeletal related procedures account for approximately one-quarter of surgical procedures performed in the United States (Seltzer JOT 2023). In addition, Medicare reimburses for roughly one-third of all orthopaedic procedures (Payne Am J Orthop 2015). One of the largest contributors to the overall cost of orthopaedic procedures is implant cost. On average implants attribute to 43-50% of procedure costs, and in some cases up to 87% of costs (Robinson JBJS 2012). Implant selection is also largely influenced by surgeons, although many are not aware of implant cost (Streit, Okike). With implants accounting for a large

proportion of overall cost, and being heavily determined by surgeons, implant-related cost reduction strategies such as using generic implants are critical to lowering costs in orthopaedic surgery.

Generic implant use has been shown to generate an average cost-savings of 49%, and in some cases up to 73% in orthopaedic trauma procedures (Kleinsmith COP 2024). Despite the reduction in cost related to generic implant use, it appears that there is still some concern among surgeons and patients over their quality and safety. One survey reported that 52% of the public see the value of generic implants, however only 26% would want them used in their surgery (Miner Ach Bone Surg 2022). Regarding surgeons, an OTA member survey found that many are aware of generic implants (73%), but only 26% use them in practice (Althausen 2016 JOT). Prior literature has compared generic cephalomedullary nails (CMNs) to brand name CMNs and found no difference in 6-month clinical and radiographic outcomes (Khoo JAAOS 2022, Kleinsmith 2024). Although this has been demonstrated in other injury patterns, there is a paucity of literature surrounding differences in cost and clinical outcomes associated with generic implant use in distal radius fracture (DRF) open reduction and internal fixation (ORIF).

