DRFs are a prime target for generic implant implementation, due to the relatively high incidence of DRFs (634,000 annually) (Mauk Orthop Clin North America 2018), and the substantial amount spent by Medicare each year on DRF management (\$385-\$535 million) (Ray JBMR 1997, Burge JBMR 2007). The purpose of this study was to assess for differences in implant cost, surgical characteristics, and 90-day clinical outcomes between patients treated with generic volar locking plates (VLPs) and conventional VLPs in the setting of a DRF. We hypothesized that there would be no difference in surgical characteristics (e.g., tourniquet times) or clinical outcomes (e.g., reoperation), however there would be reduced cost in the generic VLP group.

4. Approach

a. Study design

- i. This will be a prospective randomized controlled trial within Healthpartners in the greater Minneapolis area in Minnesota, to compare primary outcomes of subjects between generic and conventional volar locking plates in distal radius fracture patients. Group selection will be randomized month to month with generic plates being used one month and conventional plates the next.

i. Inclusion

1. >18 years old
2. Isolated DRF
3. Medical need for surgical fixation with a volar locking plate

ii. Exclusion

1. No VLP used
2. Additional fixation used
3. Injury was non-isolated (polytrauma)
4. < 18 years old
5. Open fracture

- b. Data collection process
 - i. Identify patients within HealthPartners who meet inclusion criteria who are determined to need distal radius ORIF
 - 1. Patients meeting inclusion criteria will be identified by the included surgeons on the study
 - ii. Consent
 - 1. Written informed consent for surgery will be obtained by the attending surgeon, however no additional consent will be needed as this is an FDA approved device
 - iii. Data sources needed for this study
 - 1. Chart Review for patient age, gender, height and weight
 - 2. Chart review for mortality, reoperation, readmission
 - 3. Chart review for implants, tourniquet time, estimated blood loss
 - 4. Implants will be cross referenced with institutional charge master database to obtain cost.
 - iv. Process steps for data acquisition
 - 1. Data to be obtained by chart review after completion of the study.
- c. Intervention, treatments
 - i. Patients will be randomized by month with patients during one month receiving generic implants and the following month they receive conventional implants.

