 - ii. All other standards of care remain equal between the groups.
- d. *Outcomes/endpoint and other variable definitions, and instruments used*
 - i. 90-day reoperation
 - ii. 90-day readmission
 - iii. 90-day mortality
 - iv. Implant cost
 - v. Estimated blood loss
 - vi. Tourniquet Time
- e. *Statistical analysis plan*
 - i. T-Tests and Chi-square of Demographic Data
 - ii. Chi-square of primary outcomes
 - 1. 90-day reoperation rate
 - 2. 90-day readmission rate
 - 3. 90-day mortality rate
 - iii. T-Test of Secondary Outcome Measures between subject groups
 - 1. Implant cost
 - 2. Tourniquet time
 - 3. Estimated blood loss
 - iv. Power analysis or statement of precision
An a priori power analysis was conducted to estimate the minimum sample size needed to adequately detect a difference in reoperation rates with a large effect size (Cohen's $d=0.8$). At a Type I error rate of 0.05, a power of 80%, and a 1:1

group allocation, the estimated sample size was 36 patients (18 generic VLPs vs. 18 conventional VLPs).

v. Strengths

1. Blinding of patients
2. Use of FDA approved devices
3. Randomizing of patients
4. Adequate qualified staff members to conduct the study
5. Surgeons will be adequately trained and reminded on the protocol and their specific research related duties.
6. High-volume surgeons who regularly treat distal radius fractures
7. Conservative effect size estimates

vi. Limitations

1. Surgeons are not blinded
2. Only early follow-up (90 days)
3. No patient reported outcomes included

5. Setting/Environment/Organizational feasibility

- a. This study will be conducted at Healthpartners within Minneapolis metropolitan area
- b. This HealthPartners setting has an appropriate patient population to carry out the proposed study.
- c. The orthopedic department leadership has been engaged in development and approval of this study

6. Risks and Benefits

- a. Potential risks
 - i. No different than associated risks of undergoing a standard DRF ORIF.
- b. Benefit to society
 - i. Being able to validate the use of cheaper implants to save cost for patients and healthcare systems.

7. Data Confidentiality and Privacy

- a. In order to secure patient confidentiality and data security, all data will be de-identified. All patients will be assigned a research identification number (not their MRN) that cannot be associated with their name, birthdate, or other identifying information.

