- b. Patient information will only be accessed via secure servers for TRIA and on encrypted password-protected computers. If it is necessary to transmit patient data, it will be transmitted in the de-identified format, using only patient research identification numbers.
- c. At the end of the study, the electronic files will be permanently deleted and patient identifiers will be removed.

8. Timeline

- a. August 2022: IRB submission
- b. September 2022: IRB approval
- c. October 2022: Protocol implementation
- d. April 2023: Patient enrollment closes
- e. May 2023: Data analysis
- f. July 2023: Manuscript preparation

- g. July 2023: Manuscript submission
- 9. Dissemination/Sharing Results/Integration and Impact
 - a. We do plan on publishing to peer reviewed orthopedic journals such as;
 - i. The Journal of Bone and Joint Surgery
 - ii. Clinical Orthopedics and Related Research
 - iii. Journal of Orthopedic Trauma
 - b. We plan to disseminate the information on a local and regional level by presenting at;
 - i. University of Minnesota Grand Round
 - ii. Minnesota Orthopedic Society poster presentation
 - iii. Mid-America Orthopedic Society poster presentation
 - c. Results will be shared with HealthPartners

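### The arm follows the calendar month in which the plate is used and no earlier date fixes it, so scheduling near a month boundary could decide which plate a patient gets.

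*Combined protocol and SAP*

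**What the plan says.** Section 4.a (study design) describes the allocation as "Group selection will be randomized month to month with generic plates being used one month and conventional plates the next". Section 4.c.i repeats the rule in terms of patients: "Patients will be randomized by month with patients during one month receiving generic implants and the following month they receive conventional implants". Neither section names the date that places a patient in a month, and neither has a rule for patients whose care spans two months.

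Section 4.b.i gives recruitment to the surgeons: "Patients meeting inclusion criteria will be identified by the included surgeons on the study". The patients concerned are those already judged to need fixation, so identification comes before the operation. The limitations in Section 4.e.vi state "Surgeons are not blinded" but draw no consequence for allocation. The strengths in Section 4.e.v include randomization.

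The listed chart data (Section 4.b.iii) are age, gender, height, weight, the three 90-day outcomes, implants, tourniquet time and blood loss. Fracture severity, presentation date and surgery date are not listed. Section 4.e plans unadjusted t-tests and chi-square tests.

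**The concern.** A plate is used on the day of surgery. Under a rule that ties the arm to plates in use that month, the surgery date therefore determines the arm, and that date is not a fixed attribute of the patient. As an illustration, a patient identified on 27 November could be operated on on 30 November with one plate or on 2 December with the other, and both would comply with the rule.

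The alternation tells every surgeon what the next month brings. This problem is separate from the order of the months. Even if the sequence were drawn at random, the link between patient and month would stay movable once the plates for the months concerned were known.

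If timing were related to prognosis, differences in reoperation, readmission or tourniquet time could come from scheduling and not from the implant. If harder cases drifted away from the generic plate, the generic arm would look better than it should. That would favour the hypothesised absence of a clinical difference (end of Section 3) and could hide harm.

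**Working it through.** **What the text fixes and what it leaves open**

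- Index date: Section 4.a, "generic plates being used one month and conventional plates the next", points to month of surgery. Section 4.c.i, read alone, could also mean month of identification. No sentence names injury, presentation or decision to operate.
- Who knows the arm: the surgeons, who are unblinded, for this month and the next.
- Who sets the surgery date: not stated. Surgeon influence is an assumption that nothing in the text rules out.
- Motive: mixed. Section 1 says many surgeons "have no preference for one implant company's plate over another"; Section 3.a says "there is still some concern among surgeons and patients over their quality and safety".

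**Upper bound on the number of patients exposed**

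The plan gives no figure on this point, so there is none to reproduce. The total of 36 (18 per arm, Section 4.e.iv) serves only as a denominator; whether it is adequate is a separate question.

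Inputs from Section 8: "October 2022: Protocol implementation", with enrollment closing in April 2023. Counting both months in full:

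31 + 30 + 31 + 31 + 28 + 31 + 30 = 212 days, 7 months, 6 internal month boundaries.

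Assumptions: uniform accrual, and an interval of D days from identification to surgery. The documents give no value for D, so a range is shown.

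Share of patients whose window crosses a boundary = 6 × D / 212:

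- D = 3: 18/212 = 8.5%, or 3.1 of 36
- D = 7: 42/212 = 19.8%, or 7.1 of 36
- D = 14: 84/212 = 39.6%, or 14.3 of 36

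If cases are held over a boundary only when that brings them into one favoured arm, 3 of the 6 boundaries count (3 × D / 212). The numbers halve to about 1.5, 3.6 and 7.1 of 36.

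If accrual stops at the end of March (182 days, 5 boundaries), 5 × D / 182 gives 3.0, 6.9 and 13.8 of 36, so the result barely depends on the closing date.

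**What one moved patient does**

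One event in an arm of 18 is 1/18 = 5.6 percentage points. Suppose each arm has one event, 1/18 v 1/18, a difference of 0. Moving one of those two patients to the other arm gives 2/19 v 0/17, a difference of 10.5 percentage points.

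**The case against.** The strongest reply is that the documents establish an undefined index date and little more. They do not say that surgeons choose the operating date or how long patients wait. Section 4.c.i can be read as month of identification, and on that reading the late-November patient has only one compliant plate. These points stand. Surgeon influence is therefore labelled an assumption here, and month of surgery is given as the natural reading of Section 4.a, not the only one.

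Motive is also uncertain. Many surgeons are said to be indifferent between companies, some in this health system already use the generic plate, and Section 4.e.v promises training and reminders on the protocol. Against that, Section 3.a reports surgeon concern about generic implants. The evidence points both ways, so no likelihood of steering can be claimed.

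A reader might infer that the plan could not detect steering at all. That goes too far. Moving frailer patients could show as an age difference in the planned demographic tests, although weakly at this sample size. Excluding polytrauma, open fractures and cases with additional fixation also narrows the scope for moving harder cases. What remains is that fracture severity and both dates are missing from the listed data.

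A reader might also take 14 of 36 as the number of patients misallocated. It is a ceiling under an assumed 14-day interval, and it includes every patient whose window happens to span a month end, most of whom may be scheduled without regard to the plate. Only discretionary moves related to prognosis would bias the comparison.

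**Conclusion.** The concern holds in a limited form. The allocation rule names no date before surgery that fixes the arm. The people who identify patients know the current and the coming plate. If they have any influence over the surgery date, a patient near a month boundary can end up in either arm while the protocol is followed. The plan has only weak means of noticing.

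The size is at most about 3, 7 or 14 of 36 patients for assumed intervals of 3, 7 or 14 days under uniform accrual, and about half that if moves favour one arm. With 18 per arm, even one moved patient with an event matters.

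A reader might conclude that surgeons will steer patients, or that the results are biased. The documents do not support that: they show an opportunity, with mixed evidence on motive. The point should be corrected because the remedy is cheap and the present rule leaves the allocation open to influence.

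**What to change.** - **Sections 4.a and 4.c:** set the arm by the calendar month of one index date, the first presentation for the fracture recorded in the chart. The patient keeps that assigned plate type whenever surgery takes place. Use one date only: injury and presentation can fall in different months and give opposite arms.
- **Section 4.b.iii:** add the presentation date and the surgery date to the chart data.
- **Section 4.e:** compare groups by assigned month. Report how many patients had surgery in a different month from presentation, and how many received the non-assigned plate.

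The cost is a sentence in each of Sections 4.a and 4.c, two dates in a chart review that is already planned, and two counts in the report. The downside is that both plate types must be available for patients carried over from the previous month. That creates some opportunity for crossover, which is why the count of non-assigned plates is needed. If enrollment is already complete, the two dates may still be recoverable from the charts and would allow the same comparison as a sensitivity analysis.

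This closes the scheduling route only. Surgeons would still know the arm when they identify patients. Selection could also still occur through the exclusions for cases without a volar locking plate or with extra fixation, which can be decided at surgery.

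### The plan aims to show similar outcomes, but its only primary analysis is a difference test with no interval, margin or rule for reading a non-significant result

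*Combined protocol and SAP*

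**What the plan says.** The combined protocol and SAP asks for two kinds of evidence.

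- **Difference.** The first primary aim (section 2.a) is "To determine if there is any difference in 90-day reoperation rate between patients treated with a generic or conventional volar locking plate", and the aims for readmission and mortality are worded the same way. Section 3 says "The purpose of this study was to assess for differences in implant cost, surgical characteristics, and 90-day clinical outcomes". The power statement (4.e.iv) sets out to "estimate the minimum sample size needed to adequately detect a difference in reoperation rates" and arrives at 18 patients per arm.
- **Similarity.** The title asks "Do Generic Volar Locking Plates Provide Similar Outcomes at a Reduced Cost". The hypothesis in section 3 reads: "We hypothesized that there would be no difference in surgical characteristics (e.g., tourniquet times) or clinical outcomes (e.g., reoperation". The Summary says "Validation of its safety and efficacy on a larger scale could support its adoption as a universal stand of practice". Section 6.b gives validation of cheaper implants as the benefit to society.

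The analysis listed for the three 90-day outcomes in 4.e.ii is, in full, "Chi-square of primary outcomes" followed by the outcome names. The document contains no risk difference, confidence interval, non-inferiority or equivalence margin, or statement of how a non-significant result will be read. Section 4.e.iv is headed as a power analysis or statement of precision, but it contains only a power calculation.

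**The concern.** The investigators expect a null result and intend to use it to support adoption. A chi-square test can give evidence against equal rates. When it fails to do so, it does not say how large a difference the data still allow. A non-significant result is what a trial of equivalent plates would usually produce, and also what a small trial of clearly different plates would usually produce.

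No passage says that p>0.05 will be taken as similarity, so that reading is an inference. It is a realistic one: section 3 describes earlier studies of generic nails that found no difference, then refers to the finding as having been demonstrated. The limitations in 4.e.vi do not warn that a null result may be uninformative. At stake is a system-wide recommendation made while the data remain compatible with a large excess of reoperations, readmissions or deaths.

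**Working it through.** **Inputs.** From 4.e.iv: 18 per arm as a stated minimum, and α = 0.05. The documents give no event rate and no margin, so any used below are assumptions. Differences are generic minus conventional, and patients are treated as independent.

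**The plan's own figure.** The 36 does not reproduce from d = 0.8 and 80% power. Two-sided, n per arm = 2(1.960 + 0.842)²/0.8² = 24.5, so 25. One-sided, 2(1.645 + 0.842)²/0.8² = 19.3, so 20. That is a separate issue; 18 per arm is used here as stated.

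**Interval method.** For each arm take the Wilson limits l and u. With p₁ generic, p₂ conventional and d = p₁ − p₂, the Newcombe limits are

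- lower: d − √[(p₁ − l₁)² + (u₂ − p₂)²]
- upper: d + √[(u₁ − p₁)² + (p₂ − l₂)²]

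With zero events in both arms these reduce to ±z²/(n + z²). At n = 18: 3.841/21.841 = 0.176.

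Worked case, 3 v 0 events: p₁ = 0.167 with Wilson limits 0.058 and 0.392; p₂ = 0 with limits 0 and 0.176.

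- lower: 0.167 − √(0.108² + 0.176²) = −0.040
- upper: 0.167 + (0.392 − 0.167) = 0.392
- Pearson χ² = 3.27, p = 0.070

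| Events at 18 per arm (generic v conventional) | Chi-square p (uncorrected) | 95% interval, points |
|---|---|---|
| 0 v 0 | cannot be computed | −17.6 to +17.6 |
| 1 v 0 | 0.310 | −12.6 to +25.8 |
| 1 v 1 | 1.00 | −20.7 to +20.7 |
| 3 v 0 | 0.070 | −4.0 to +39.2 |

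**All possible results.** There are 19 × 19 = 361 pairs of event counts at 18 per arm. The narrowest symmetric band that contains both limits is ±17.6 points (0 v 0, or 18 v 18), so no result puts both limits within ±17. An upper limit below an illustrative 10 points requires at least 2 fewer events in the generic arm; 0 v 2, for example, gives +8.2.

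**An empty table is plausible.** At an assumed common rate of 2%, the chance of no events among 36 patients is 0.98³⁶ = 48%.

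**Larger enrolment.** Because 36 is a minimum, the same quantities were computed at larger sizes. The last column assumes true rates of 15% v 5% and enumerates the uncorrected chi-square exactly.

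| Per arm | 0 v 0 interval, points | Chance of p>0.05 at 15% v 5% |
|---|---|---|
| 18 | ±17.6 | 87% |
| 36 | ±9.6 | 68% |
| 50 | ±7.1 | 61% |
| 100 | ±3.7 | 32% |

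The last column mainly reflects sample size. It is shown because it tells the reader how little p>0.05 says on its own.

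**The case against.** The strongest reply is that the operative parts of the plan agree with each other: aims, purpose, sample size and test all concern a difference. The similarity language sits in a title phrased as a question, a hedged sentence in the Summary and a benefit statement. The hypothesis is a prediction, not a decision rule, and no passage claims equivalence or non-inferiority. A brief SAP that is silent on intervals does not prove they would go unreported. The widths above also come largely from the small sample, and the 10-point limit and the 15% v 5% rates have no source in the documents.

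Much of this stands. Chi-square answers the aims as worded and should be kept for them. The plan does not prescribe a misreading; it fails to guard against one. The figures illustrate the problem and do not set thresholds. A single 10-point margin would be hard to defend for mortality in particular.

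It does not remove the point. The expected result is null, and the stated use needs evidence that a null chi-square cannot give. The gap persists at any sample size: a large trial reported by chi-square alone would still not state the excess risk that the data leave open.

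**Conclusion.** The concern holds. The planned primary analysis can address whether a difference was detected, but not whether the plates give similar outcomes. This affects all three primary outcomes and the main conclusion, so it needs correcting. At the stated minimum size, even the most favourable symmetric result, no events in either arm, leaves differences of up to 17.6 points in either direction.

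The absence of an interval, margin and reading rule rests on the text alone. The widths assume 18 per arm and independent patients. Allocation is by calendar month ("Group selection will be randomized month to month with generic plates being used one month and conventional plates the next"), so positive correlation within months would make these intervals too narrow.

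**What to change.** In section 4.e.ii:

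1. Make the main result for each 90-day outcome the risk difference, generic minus conventional, with a small-sample 95% interval such as Newcombe. Keep chi-square as a secondary p-value for the aims about any difference.
2. State that p>0.05 will not be read as similarity.
3. Call the generic plate non-inferior on an outcome only if the upper limit lies below a margin that the investigators justified before outcome data were seen. Call the plates similar only if both limits lie within such margins. Say whether all three outcomes must meet their margins, which needs no alpha adjustment, or may be claimed separately, with a named multiplicity method such as 98.3% intervals (Bonferroni for three).
4. If no margin was set in advance, report the interval only and call the result inconclusive or preliminary. This may be the only route left: section 8 places data analysis in May 2023, and section 3 already cites 2024 literature.
5. Tabulate patients and events by month and arm, and note that intervals treating patients as independent may be too narrow. Do not use an assumed intracluster correlation as a pass/fail gate.

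Items 1, 2 and 4 are the core repair. Item 3 applies only if a similarity or non-inferiority claim is wanted, and item 5 is a supporting safeguard.

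**Cost.** The core repair takes SAP wording and a few lines of analysis, with no new patients or data. Its drawback is a probable verdict of inconclusive at 36 patients. A margin-based claim would need more patients. The table gives the smallest number per arm at which the upper limit falls below an illustrative margin, with independent patients:

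| Observed events | 10-point margin | 5-point margin |
|---|---|---|
| 0 v 0 | 35 | 73 |
| 1 v 1 | 43 | 91 |
| 1 v 0 | 53 | 110 |
| 0 v 0, 98.3% interval | 52 | 109 |

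At 18 per arm, the 98.3% interval at 0 v 0 is ±24.2 points. Any positive within-month correlation raises the numbers in the table.

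### Section 4.e.ii names only an unspecified chi-square test for the three binary primary outcomes, so at 18 per arm a nominally significant result can rest on the approximation or a software default (minor)

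*Combined protocol and SAP*

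**What the plan says.** Section 2.a makes three binary outcomes primary: reoperation, readmission and death, each within 90 days. The mortality aim, for example, reads "To determine if there is any difference in 90-day mortality rate between patients treated with a generic or conventional volar locking plate".

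Section 4.e.ii gives the whole analysis of these outcomes as "Chi-square of primary outcomes" and then lists the three rates. Nothing is said about a continuity correction, an exact alternative, small expected counts, a table with no events, or confidence intervals.

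Section 4.e.iv gives the planned size: "the estimated sample size was 36 patients (18 generic VLPs vs. 18 conventional VLPs". It presents this as a minimum, and the Timeline (section 8) ends recruitment by date: "April 2023: Patient enrollment closes". The final number could therefore be larger. No event rate is given for any primary outcome.

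**The concern.** The Pearson chi-square p-value is a large-sample approximation. Its usual working condition is an expected count of at least 5 in every cell. Death, readmission and reoperation within 90 days of surgery for a closed, isolated wrist fracture may well be uncommon, and 18 patients per arm then yield only a handful of events.

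Two things follow. Uncorrected chi-square can fall below 0.05 in a table where exact tests do not. And because the plan does not settle the continuity correction, two analysts who both follow it can reach opposite verdicts on the same data. The study is meant to inform wide adoption of the generic plate, so a few reoperations in one arm could be reported as a significant difference that no exact test supports. At the other extreme, a table with no events has no chi-square statistic, and the plan has no rule for it.

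**Working it through.** **Inputs.** From section 4.e.iv: 18 per arm, type I error 0.05. Sidedness is not stated; two-sided is assumed. Event rates are not given; 1% to 30% is assumed here, equal in both arms.

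**The plan's own figure.** Section 4.e.iv bases the 36 on power to "detect a difference in reoperation rates with a large effect size (Cohen's $d=0.8"). The normal formula n = 2(z_α + z_β)²/d² gives 2(1.960 + 0.842)²/0.64 = 24.5, so 25 per arm two-sided. One-sided it gives 2(1.645 + 0.842)²/0.64 = 19.3, so 20 per arm. Neither gives 18. That is a separate issue; 18 per arm is taken as planned below.

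**1. Expected counts.** At 18:18 the expected events per arm are T/2, where T is the total number of events. T/2 ≥ 5 needs T ≥ 10 of 36. The chance of T ≤ 9, from Binomial(36, p), is over 99.9% at p = 5%, 99.8% at 10% and 96.5% at 15%.

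**2. No events.** The chance is (1 − p)^36: 0.99^36 = 70%, 0.98^36 = 48%, 0.95^36 = 16%, 0.90^36 = 2%. The chi-square statistic is then 0/0.

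**3. One table by hand, 0/18 against 4/18.**
- Uncorrected: 36 × (18 × 4)² / (18 × 18 × 4 × 32) = 186,624 / 41,472 = 4.50, p = 0.034.
- Corrected: 36 × (72 − 18)² / 41,472 = 104,976 / 41,472 = 2.53, p = 0.112.
- Fisher: 2 × C(18,4)/C(36,4) = 2 × 3,060 / 58,905 = 0.104.
- Boschloo: 0.065.

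**4. Neighbouring tables at 18:18.**

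| Events | Uncorrected | Corrected | Fisher | Boschloo |
|---|---|---|---|---|
| 0 v 3 | 0.070 | 0.228 | 0.229 | 0.133 |
| 0 v 4 | 0.034 | 0.112 | 0.104 | 0.065 |
| 0 v 5 | 0.016 | 0.054 | 0.046 | 0.029 |
| 1 v 6 | 0.035 | 0.092 | 0.088 | 0.048 |
| 2 v 8 | 0.026 | 0.063 | 0.060 | 0.029 |

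The correction alone changes the verdict in four of these five tables (all but 0 v 3). Of the five, 0 v 4 is the only one significant by uncorrected chi-square that neither exact test supports.

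**5. Overall type I error at 18:18, by full enumeration.**

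| Assumed rate | Uncorrected chi-square | Fisher | Verdicts differ |
|---|---|---|---|
| 2% | 0.05% | 0.003% | 0.05% |
| 5% | 0.88% | 0.12% | 0.75% |
| 10% | 3.34% | 0.92% | 2.4% |
| 20% | 4.75% | 2.05% | 2.7% |
| 30% | 4.99% | 2.17% | 2.8% |

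The last column is the difference of the two before it.

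**6. Rejection rate given the total number of events (18:18, no true difference).** Uncorrected chi-square: 0% for 0 to 3 events, 10.4% for 4, 4.5% for 5, 1.9% for 6, 8.8% for 7, 4.1% for 8, 1.8% for 9, 6.0% for 10. Fisher equals chi-square at 5, 6, 8 and 9 events, and is 0%, 0.8% and 0.7% at 4, 7 and 10.

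**The case against.** A reader might infer that the chi-square test inflates the false-positive rate of the trial, or that the primary verdicts will depend on the choice of test. The documents and the arithmetic do not support either. At 18:18 the overall type I error stays at or below 5% up to a rate of about 30%. With 0 to 3 events neither chi-square nor Fisher can reject, and that covers 99.4% of trials at a 2% rate and 90% at 5%. If the true rates are equal, the two tests disagree in under 1% of trials at a 5% rate. The conditional rates of 10.4% and 8.8% hold only at 4 and 7 events; at 5, 6, 8 and 9 events chi-square rejects exactly as often as Fisher. Judging a test conditionally or unconditionally is partly a matter of statistical preference.

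A reader might also argue from unequal arms. Section 4.a says "Group selection will be randomized month to month with generic plates being used one month and conventional plates the next", and October to April is seven months if April counts in full, which with even accrual splits 36 patients about 21:15. There 0/21 against 3/15 gives 0.032 by uncorrected chi-square and 0.064 by Fisher. But the plan states 1:1 allocation and gives no monthly accrual, and even at 21:15 the overall size is 1.4% at a 5% rate and 4.7% at 20%. Sizes above 5% appear only for splits that no document gives (20:16 and 22:14, at an assumed 20% rate).

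Finally, an exact test cannot supply missing information: at 18 per arm Fisher needs 5 events against 0 to reach 0.05. For a study that expects no difference, a more conservative test makes the hoped-for result easier to obtain. This stands, and it is why an interval matters more than the p-value.

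What remains is narrower: the named test is incompletely specified, has no value for an empty table, and in some tables gives a significant p-value that exact tests do not support.

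**Conclusion.** The concern holds in a limited form, and its severity is minor. Section 4.e.ii leaves the continuity correction and the handling of sparse or empty tables open, at a sample size where expected counts will almost certainly fall below 5 if event rates are 10% or less. The consequence is confined to individual p-values and to undefined results. The clearest case is 0 against 4 events, where only the uncorrected test gives p < 0.05. It is not an inflated overall error rate.

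This rests on assumed event rates, since the documents give none, on two-sided testing, and on 18 per arm. A larger final sample helps little if events are rare: at 50 per arm and a 5% rate, the chance of an expected count below 5 is still 97%. Allocation by calendar month and the sample-size calculation are separate issues, and both are larger than the choice of test.

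**What to change.** In section 4.e.ii, replace chi-square for the primary outcomes with one named exact test, two-sided at 0.05: Boschloo's, or Fisher's if the sponsor prefers the more familiar test. For each primary outcome, add the number of events and patients per arm and the risk difference with an exact 95% confidence interval, naming the interval method. State that these are reported even when an outcome has no events.

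The interval keeps an empty or near-empty table from being read as evidence of similarity. With 0 events in 18 patients, the upper limit of the two-sided exact 95% interval is 1 − 0.025^(1/18) = 18.5%.

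The cost is a line or two of text and some power, with a larger loss under Fisher than under Boschloo: Boschloo retains p < 0.05 at 1 v 6 and 2 v 8, where Fisher does not. Both tests treat patients as independent, so this change does not address allocation by month or the sample size.
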